4.0 Study Design and Randomization

4.1 Study Design and Randomization (P1, EHR-based antibiotic decision support)

Effectiveness of the EHR-based antibiotic decision support application for promoting guideline-concordant antibiotic prescribing in children presenting for emergency care will be evaluated in a pragmatic, cluster randomized crossover study conducted over a period of 18 months that includes two respiratory seasons. Our institutions possess demonstrated experience in the execution of these pragmatic designs.¹⁷⁻²¹ Crossover will occur each month in a randomly determined sequence within each hospital. To ensure balanced representation of each arm in periods of both low and high pneumonia prevalence, randomization will occur in 3 permuted blocks (size=6). The cluster-randomized crossover design also improves efficiency and reduces potential problems related to cluster imbalance when using a small number of clusters.⁶⁷ The antibiotic decision support application will be provided to those randomized to the intervention arm, whereas the control arm will receive usual care. Due to the nature of the intervention, blinding of treating providers will not be possible. Importantly, since this is a trial focused on provider behavior, all children will receive standard of care management. All treatment decisions will be made by the clinical providers and will not be restricted or altered in any way.

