## **6.2 Sample Size and Power**

### **6.2.1 Phase 1**

Based on ED and hospitalization data from our hospitals during the conduct of the EPIC study, we anticipate nearly 2000 total children with pneumonia will be evaluated annually during the conduct of these studies. Assuming conservatively that data for 750 children are enrolled in each arm, and 30% guideline-concordant antibiotic use in the usual care arm (based on our prior study of antibiotic use in the EPIC cohort), we will be able to detect an absolute difference of  $\geq 6.8\%$  in guideline-concordant prescribing at an alpha level of 0.05 with 80% power. Effective sample size may be reduced due to the cluster randomized nature of the study (a conservative estimate for effective sample size would be around 500 children in each arm).

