## **6.3 Randomization**

### **6.3.1 Phase 1**

During the 18-month study period, EHR-based antibiotic decision support will be active monthly (4-week blocks) based on the cluster randomized scheme at each hospital. To ensure balanced representation of each arm in periods of both low and high pneumonia prevalence, randomization will occur in 3 permuted blocks (size=6). The antibiotic decision support application will be provided to those randomized to the intervention arm, whereas the control arm will receive usual care. Participants enrolled during the month with antibiotic decision support will be assigned to the intervention arm, and participants receiving usual care will be in the control arm. Participants will be blinded to the treatment assignments and study staff and providers will not be blinded to treatment arm assignments due to the nature of the interventions.

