### **10.1 Primary Objective**

The primary objective (PO 1) of the study is to compare proportions of participants exclusively receiving guideline-concordant 1st line antibiotic therapy during the first 24 hours of care with or without EHR-based decision support in children 0.6-17 years of age presenting for emergency care. The hypothesis for this primary objective is that the proportion of participants exclusively receiving guideline-concordant 1st line antibiotic therapy during the first 24 hours of care is higher in the group receiving EHR-based decision support vs. the group receiving usual care. This information is captured through chart review and entered in the REDCap database. The antibiotics received by a participant is concordant yes (1) or no (0) based on Appendix 1 table, for this analysis.

The proportions will be compared between the intervention arm versus the control arm using a Cochran-Mantel-Haenszel method in a stratified analysis by site to control for two sites at the alpha 0.05 level. The proportion difference and corresponding 95% confidence interval for concordance of antibiotics with or without adjusting for sites will also be calculated.

We will use a hierarchical and mixed effects logistic regression model, a complex analytic approach which offers flexibility regarding model assumptions and incorporation of cluster-level and individual-level covariates. The outcome is proportions of participants exclusively receiving guideline-concordant 1st line antibiotic therapy during the first 24 hours of care and the main exposure variable is intervention vs. usual care. The month of each participant enrolled will be treated as a random effect. We will also use a weighted, cluster-level logistic regression to compare guideline-concordant antibiotic prescribing between groups. In this analysis, data for each cluster are collapsed into a single summary measure, and the summary measures are then analyzed as if they were raw data, facilitating simple data reporting and interpretation. Important baseline covariates (e.g., age, sex, race, site, season, frequency of bacteremia and other pneumonia-related complications) will also be assessed and included as model covariates.

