### **10.2 Secondary Objectives**

There are five secondary objectives for this study.

- a) The first secondary objective (SO 1) is to compare proportions of participants exclusively receiving guideline-concordant antibiotic therapy for the entire episode, by EHR-based decision support or usual care.

The analysis is similar to primary objective 1 though the proportion of participants exclusively receiving guideline-concordant antibiotic therapy for the entire episode is the outcome.

- b) The second secondary objective (SO 2) is to compare proportions of participants receiving any guideline-concordant antibiotic therapy during the first 24 hours of care, by EHR-based decision support or usual care.

Proportions of participants with any concordant antibiotic therapy during the first 24 hours of care (yes or no) will be compared between intervention and control arms using a Chi-square test. Proportions and difference of proportions between intervention and control arms will be reported along with their 95% CIs.

A mixed effects logistic regression model will be conducted. The outcome is any concordant antibiotic therapy (yes or no) and covariates under the consideration will be similar to the ones listed in the primary objective analysis 10.1.

- c) The third secondary objective (SO 3) is to compare proportions of participants receiving guideline-concordant for the entire episode, by EHR-based decision support or usual care.

The analysis is similar to secondary objective 2 though the proportion of participants using any of concordant antibiotic therapy for the entire episode is the outcome.

- d) The fourth secondary objective (SO 4) is to compare proportions of participants having ED revisits and hospitalizations within 72 hours of the index discharge, by EHR-based decision support or usual care.

Proportions of participants having ED revisits or hospitalizations within 72 hours of the index discharge will be compared between intervention and control arms using Chi-square tests. Proportions and difference of proportions between intervention and control arms will be reported along with their 95% CIs.

Two mixed effects logistic regression models will be conducted. The outcomes are ED revisits (yes or no) and hospitalizations (yes or no) within 72 hours of the index discharge and covariates under the consideration will be similar to the ones listed in the primary objective analysis 10.1.

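### The Phase 1 cluster-level and mixed models omit the hospital-by-block strata used to randomise, so they lose power if prescribing drifts by about 10 points or more over the 18 months

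*SAP*

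**What the plan says.** Protocol 4.1 sets the unit of allocation: "Crossover will occur each month in a randomly determined sequence within each hospital". SAP 6.3.1 adds that "randomization will occur in 3 permuted blocks (size=6", with the purpose "To ensure balanced representation of each arm in periods of both low and high pneumonia prevalence". Two hospitals and three blocks make six randomisation strata and 2 x 18 = 36 hospital-periods.

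SAP 10.1 plans three comparisons for the primary outcome:

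- a patient-level test "using a Cochran-Mantel-Haenszel method in a stratified analysis by site to control for two sites at the alpha 0.05 level";
- a mixed logistic model with enrolment month as a random effect, without saying whether this is calendar month or hospital-month;
- a weighted cluster-level logistic regression.

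The covariates are "Important baseline covariates (e.g., age, sex, race, site, season, frequency of bacteremia and other pneumonia-related complications". Block and calendar time are not named here or in Protocol 8.2.

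For SO2 in SAP 10.2, proportions "will be compared between intervention and control arms using a Chi-square test", with no site stratification; SO3-SO5 and EO2-EO6 follow the same pattern. SO1 follows the primary analysis, so it keeps the site-stratified test. The outcomes tested by chi-square also get mixed models whose covariates resemble those of 10.1.

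Calendar time is used only in the contamination analysis of Protocol 8.2, which models monthly proportions by arm and compares them with a historical trend. It does not adjust the treatment comparison and does not appear in the SAP.

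**The concern.** Blocking forces each hospital to contribute three intervention and three control periods in every block. A level shift between blocks therefore cannot favour either arm, apart from differences in patient volume. An analysis gains precision from this only if it conditions on block. Without block, slow change in prescribing stays in the residual variance of any model whose error term is the hospital-period, and the reported standard error exceeds the true variability of the estimate.

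Season does not replace block. Over 18 months the first and third blocks can fall in the same season a year apart.

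A real effect could be missed in the two Phase 1 analyses that respect the clustering, and power there is already thin. At the plan's own effective sample of about 500 per arm, power for the stated 6.8-point difference is 62.6%.

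**Working it through.** **Inputs from the documents.** SAP 6.2.1: "Assuming conservatively that data for 750 children are enrolled in each arm, and 30% guideline-concordant antibiotic use in the usual care arm"; 80% power at alpha 0.05 for a difference of at least 6.8 points; effective sample about 500 per arm. SAP 6.3.1: blocks as above.

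**Reproducing the plan's figure.** Two-sided test, pooled variance, no continuity correction: 30% against 36.8% needs 754 per arm. At 750 per arm, power is 79.8% and the detectable difference is 6.8 points, as stated. At 500 per arm the detectable difference is 8.4 points.

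**Clustering implied by the plan.**
- Design effect = 750/500 = 1.5.
- Mean size = 1500/36 = 41.7 children per hospital-period.
- ICC = (1.5 - 1)/(41.7 - 1) = 0.0123.
- Hospital-period SD = sqrt(0.0123 x 0.30 x 0.70) = 0.051.

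**Share of drift that block removes.** For linear drift with step b per period, the variance over 18 periods is b² x (18² - 1)/12 = 26.92b². Within a block of six it is b² x (6² - 1)/12 = 2.92b². The between-block share is 1 - 2.92/26.92 = 89%.

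**Effect on the standard error.** The variance of a hospital-period proportion without drift, at mean rate 0.334, is 0.334 x 0.666/41.7 + 0.051² = 0.00534 + 0.00260 = 0.00794. With total drift D and b = D/17, the ratio of the SE without block to the SE with block is sqrt[(0.00794 + 26.92b²)/(0.00794 + 2.92b²)].
- D = 5 points: 1.01.
- D = 10 points: sqrt(0.00887/0.00804) = 1.05.
- D = 20 points: sqrt(0.01167/0.00834) = 1.18.

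**Simulated power, without block then with site x block.** Assumptions: 36 hospital-periods, 1500 children, SD 0.051, linear drift. Linear models on proportions stand in for the logistic models. For the 6.8-point columns, high-season months have double volume. Those columns use 2,500 runs per cell (800 for the mixed model), with Monte Carlo error of about 1 to 2 points.

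| Drift (points) | Cluster-level, 6.8-point effect | Cluster-level, 8.4-point effect | Mixed, random hospital-month, 6.8-point effect |
|---|---|---|---|
| 0 | 59.2%, 58.7% | 78%, 77% | 62.0%, 62.2% |
| 5 | 60.4%, 61.3% | not run | not run |
| 10 | 55.8%, 60.5% | 74%, 77% | 60.1%, 64.2% |
| 20 | 41.3%, 58.1% | 62%, 76% | 43.5%, 60.1% |

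A separate run of 3,000 simulations per cell, with 3:1 peak-to-trough volumes and an 8.4-point effect, gave 72% and 76% at 10 points, and 59% and 75% at 20.

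Under the null at 20 points of drift, the cluster-level model without block reports a mean SE of 0.0365 against a true SD of 0.0312 and rejects 2.2% of the time. With site x block the figures are 0.0294, 0.0309 and 6.1%.

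**Season and calendar month.** A four-level season term in place of block gives 52.5% at 10 points and 37.5% at 20 (6.8-point effect), so it recovers nothing. A random calendar month shared by both hospitals shrinks the loss at 20 points (60.5% without block, 67.1% with). Its null rejection there is 8.9% and 10.6%, because the simulated variation is specific to each hospital-month and a shared effect misses part of it.

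**Patient-level tests.** CMH by site has power 74.7%, 74.4% and 73.9% at 0, 10 and 20 points (6.8-point effect). Replacing site by site x block (8.4-point effect) gives 88.2% and 88.2% at 10 points, and 87.0% and 87.4% at 20. Null rejection is 12.6% and 12.5%, then 13.8% and 13.4%.

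**Site mix in the unstratified tests.** If the hospitals differ by 20 points (assumed; the documents give no hospital rates), randomisation alone gives the pooled difference an SD of about 0.6 to 1.7 points, depending on seasonality and start month.

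**The case against.** The strongest reply is that the harm misses the primary test. The site-stratified CMH is the only Phase 1 analysis that the SAP ties to alpha 0.05, and its power does not depend on drift. This stands. A reader might infer that the whole primary analysis is too wide, or that stratifying the CMH by block would help. Neither follows: block changes it by less than half a point, and its errors are too narrow because it ignores month clustering.

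Drift is also unquantified, and Protocol 8.2 describes concordant prescribing as having stayed low for years despite guidelines and order sets. A 20-point drift from a 30% base would be large. This limits the size of the point. The same section, however, takes possible contamination seriously enough to plan a trend analysis.

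The covariate list is open and season is undefined. Season coded by year would recover part of the loss (60% to 70% power at 20 points in one simulation), though it costs power at lower drift. An open list permits block but does not pre-specify it.

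On the secondary outcomes, a reader might infer that site is dropped throughout, or that site mix biases the comparison. Neither is supported. SO1 keeps the site-stratified test, and the companion models for the outcomes tested by chi-square list site. Allocation is randomised within hospital, so any site-mix imbalance is chance with mean zero.

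**Conclusion.** The point holds for the cluster-level regression and for a mixed model with a random hospital-month. Neither conditions on the strata that were used to randomise. The cost is essentially nil at 0 to 5 points of drift, about 3 to 5 points of power at 10, and about 15 at 20 (14 to 17 across the runs). Part of this gap reflects null rejection below 5% without block and slightly above it with block.

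The figures rest on assumed linear drift, the plan's implied design effect of 1.5, and linear proxies for the logistic models. The error is conservative, so it can hide an effect but does not create one. If the random effect is calendar month, the loss is smaller; SAP 10.1 leaves this open.

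The power claim does not extend to the CMH or chi-square tests. Leaving site out of the latter is a minor inconsistency with SAP 7.2, which stratifies the primary analysis by site.

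**What to change.** In SAP 10.1, add site x block as fixed effects to the Phase 1 cluster-level and mixed models, and carry this through to the secondary and exploratory models that refer back to 10.1. State that the random effect is hospital-month.

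Take block from the allocation schedule, the hospital and the enrolment date. SAP 6.3.1 says that "EHR-based antibiotic decision support will be active monthly (4-week blocks", so state whether a period is a calendar month or four weeks, because that fixes the block boundaries.

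As a minor consistency change, replace the unstratified chi-square tests and differences for SO2-SO5 and EO2-EO6 with site-stratified ones. Do not present block stratification as a remedy for the patient-level tests; month clustering there needs its own solution.

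The cost is SAP wording. At the hospital-period level, residual degrees of freedom fall from 36 - 3 = 33 to 36 - 7 = 29. Without drift, power is practically unchanged (59.2% and 58.7%).

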### **10.2 Secondary Objectives**

There are five secondary objectives for this study.

- a) The first secondary objective (SO 1) is to compare proportions of participants exclusively receiving guideline-concordant antibiotic therapy for the entire episode, by EHR-based decision support or usual care.

The analysis is similar to primary objective 1 though the proportion of participants exclusively receiving guideline-concordant antibiotic therapy for the entire episode is the outcome.

- b) The second secondary objective (SO 2) is to compare proportions of participants receiving any guideline-concordant antibiotic therapy during the first 24 hours of care, by EHR-based decision support or usual care.

Proportions of participants with any concordant antibiotic therapy during the first 24 hours of care (yes or no) will be compared between intervention and control arms using a Chi-square test. Proportions and difference of proportions between intervention and control arms will be reported along with their 95% CIs.

A mixed effects logistic regression model will be conducted. The outcome is any concordant antibiotic therapy (yes or no) and covariates under the consideration will be similar to the ones listed in the primary objective analysis 10.1.

- c) The third secondary objective (SO 3) is to compare proportions of participants receiving guideline-concordant for the entire episode, by EHR-based decision support or usual care.

The analysis is similar to secondary objective 2 though the proportion of participants using any of concordant antibiotic therapy for the entire episode is the outcome.

- d) The fourth secondary objective (SO 4) is to compare proportions of participants having ED revisits and hospitalizations within 72 hours of the index discharge, by EHR-based decision support or usual care.

Proportions of participants having ED revisits or hospitalizations within 72 hours of the index discharge will be compared between intervention and control arms using Chi-square tests. Proportions and difference of proportions between intervention and control arms will be reported along with their 95% CIs.

Two mixed effects logistic regression models will be conducted. The outcomes are ED revisits (yes or no) and hospitalizations (yes or no) within 72 hours of the index discharge and covariates under the consideration will be similar to the ones listed in the primary objective analysis 10.1.

- e) The fifth secondary objective (SO 5) is to compare proportions of participants having ED revisits and hospitalizations within 7 days of the index discharge, by EHR-based decision support or usual care

The analysis is similar to secondary objective 4 though proportions of having ED revisits and hospitalizations within 7 days of the index discharge are the outcomes.

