7.2 Outcomes (P1)

The primary outcome is the proportion of children exclusively receiving guideline-concordant 1st line antibiotic therapy during the first 24 hours of care (Table 1). For patients discharged from the ED, this will include antibiotics received in the ED as well as antibiotic

Table 1. Concordant Use Definitions for 1st Line Antibiotics¹

Disposition	<6 Years of Age	≥6 Years of Age
Home care	No antibiotics or amoxicillin	Amoxicillin
Inpatient, ward	Ampicillin/amoxicillin	Ampicillin/amoxicillin
Inpatient, ICU or complicated disease ²	Ampicillin or ceftriaxone +/- anti-staphylococcal +/- macrolide	Ampicillin or ceftriaxone +/- anti-staphylococcal +/- macrolide

ICU, intensive care unit ¹Unless specific pathogen identified or known drug allergy ²eg, empyema

prescriptions provided at discharge. For hospitalized patients, this will include therapy received during the first 24 hours of care beginning with ED triage. A patient following treatment according to table 1 will be considered as concordant, whereas deviations from these treatments will be considered discordant.

Secondary outcomes include exclusive use of concordant antibiotic therapy for the entire episode, any use of concordant antibiotic therapy during the first 24 hours of care and for the entire episode, and ED revisits and hospitalizations within 72 hours and 7 days of the index discharge. Index visit is defined as the enrollment ED visit or hospitalization through discharge.

Exploratory outcomes include time to first antibiotic, lack of antibiotics during the first 24 hours of care and for the entire episode, and changes in antibiotics after 72 hours, and death, and for hospitalized children, delayed ICU transfer, defined as >24 hours following hospitalization.

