### **4 STUDY OUTCOME MEASURES FOR PHASE 1**

#### **4.1 Primary**

- a) POM 1.1: Proportions of participants exclusively receiving guideline-concordant 1st line antibiotic therapy during the first 24 hours of care, by EHR-based decision support. Please see Appendix 1 for the concordant use definitions for 1st line antibiotics.

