#### **4.2 Secondary**

- a) SOM 1.1: Proportions of participants exclusively using of concordant antibiotic therapy for the entire episode, by EHR-based decision support or usual care.
- b) SOM 2.1: Proportions of participants using any of concordant antibiotic therapy during the first 24 hours of care, by EHR-based decision support or usual care.
- c) SOM 3.1: Proportions of participants using any of concordant antibiotic therapy for the entire episode, by EHR-based decision support or usual care.
- d) SOM 4.1: Proportions of participants having ED revisits within 72 hours of the index discharge (the enrollment ED visit or hospitalization through discharge), by EHR-based decision support or usual care.  
SOM 4.2: Proportions of participants having hospitalizations within 72 hours of the index discharge, by EHR-based decision support or usual care.

- e) SOM 5.1: Proportions of participants having ED revisits within 7 days of the index discharge, by EHR-based decision support or usual care.  
SOM 5.2: Proportions of participants having hospitalizations within 7 days of the index discharge, by EHR-based decision support or usual care.

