### **11.3 Exploratory Objectives**

There are two exploratory objectives for this study.

- a) The first exploratory objective (EO 1) is to compare the proportion of death, by EHR-based prognostic decision support or usual care.

The analysis is similar to secondary objective 2 though the proportion of death is the outcome.

- b) The second exploratory objective (EO 2) is to compare hospital length of stay among hospitalized children, by EHR-based prognostic decision support or usual care.

The Wilcoxon rank-sum test will be used to compare length of stay between intervention and control arms.

A cox regression model will be conducted. The outcome is length of stay. The covariates under the consideration will be similar to the ones listed in the primary objective analysis 11.1.

## Appendix 1

Prior B-lactam	Severe PCN allergy	Moderate to large PPE	Necrotizing or severe pneumonia	Aspiration	Outpatient	Inpatient	ICU without invasive mechanical ventilation or shock	ICU WITH invasive mechanical ventilation and without shock	ICU WITH invasive mechanical ventilation AND shock
NO	NO	NO	NO	NO	Amoxicillin	Ampicillin	Ampicillin or Ceftriaxone	Ceftriaxone	Ceftriaxone plus Vancomycin
NO	NO	NO	NO	YES	Amoxicillin/Clavulanate	Ampicillin/Sulbactam	Ampicillin/Sulbactam or Clindamycin	Ampicillin/Sulbactam or Clindamycin	Ceftriaxone plus Vancomycin
NO	NO	NO	YES	NO	n/a	Ceftriaxone plus Clindamycin or Vancomycin	Ceftriaxone plus Clindamycin or Vancomycin	Ceftriaxone plus Vancomycin	Ceftriaxone plus Vancomycin
NO	NO	NO	YES	YES	n/a	Ceftriaxone plus Clindamycin or Vancomycin	Ceftriaxone plus Clindamycin or Vancomycin	Ceftriaxone plus Vancomycin	Ceftriaxone plus Vancomycin
NO	NO	YES	NO	NO	n/a	Ampicillin	Ceftriaxone plus Clindamycin or Vancomycin	Ceftriaxone plus Clindamycin or Vancomycin	Ceftriaxone plus Vancomycin
NO	NO	YES	NO	YES	n/a	Ampicillin/Sulbactam	Ceftriaxone plus Clindamycin or Vancomycin	Ceftriaxone plus Clindamycin or Vancomycin	Ceftriaxone plus Vancomycin
NO	NO	YES	YES	NO	n/a	Ceftriaxone plus Clindamycin or Vancomycin	Ceftriaxone plus Clindamycin or Vancomycin	Ceftriaxone plus Vancomycin	Ceftriaxone plus Vancomycin
NO	NO	YES	YES	YES	n/a	Ceftriaxone plus Clindamycin or Vancomycin	Ceftriaxone plus Clindamycin or Vancomycin	Ceftriaxone plus Vancomycin	Ceftriaxone plus Vancomycin

NO	YES	NO	NO	NO	Clindamycin	Clindamycin	Clindamycin or Levofloxacin	Levofloxacin	Levofloxacin plus Vancomycin

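### Phase 1 SO 1 scores the whole episode on a first-line regimen table that conflicts with Protocol Table 1 and has no rule for later therapy

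*SAP*

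**What the plan says.** SAP 10.2 gives SO 1 no scoring rule of its own: "The analysis is similar to primary objective 1 though the proportion of participants exclusively receiving guideline-concordant antibiotic therapy for the entire episode" is the outcome. The rule it points back to is in SAP 10.1: "The antibiotics received by a participant is concordant yes (1) or no (0) based on Appendix 1 table, for this analysis". SAP 4.1 describes Appendix 1 as holding the definitions for first-line antibiotics. The SO 1 outcome measure in SAP 4.2 reads "Proportions of participants exclusively using of concordant antibiotic therapy for the entire episode"; it drops the first-line qualifier and cites no table.

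Appendix 1 has one row per combination of clinical modifiers and one column per disposition or severity level. Many cells name a fixed combination, such as "Ceftriaxone plus Clindamycin or Vancomycin".

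Protocol 7.2, Table 1, is a different table. Its ward cell is "Ampicillin/amoxicillin", its ICU or complicated-disease cell makes anti-staphylococcal and macrolide agents optional (+/-), and its footnote exempts an identified pathogen or a known drug allergy. Protocol 7.1 adds that the tool will advise considering oral treatment for ward children who are taking oral intake well.

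**The concern.** A first-line table can serve for the first 24 hours. A whole episode also contains what comes later: a switch to an oral drug, stopping one of two drugs, a change once a pathogen is known. Appendix 1 addresses none of these. If it is applied as written, some children whose treatment stayed appropriate by the protocol's own table are coded as failures.

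SO 1 is the first-listed secondary outcome. If the episode ends with the index visit, what SO 1 adds to the primary is mainly later therapy in admitted children, because Protocol 7.2 already counts ED antibiotics plus the discharge prescription in the primary for children sent home. That is the part the table handles worst. A weak SO 1 beside a positive primary could then be misread as an effect that did not last.

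**Working it through.** **1. The two tables side by side**

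| Issue | SAP Appendix 1 | Protocol Table 1 |
|---|---|---|
| Identified pathogen | No exception | Exempt (footnote) |
| Drug allergy | Severe penicillin allergy is a row modifier | Known drug allergy exempt (footnote) |
| Ward, no modifiers (base row) | Ampicillin only; amoxicillin appears under Outpatient | Ampicillin or amoxicillin |
| Second agents, ICU or complicated disease | Fixed *plus* regimens in many cells | Optional (+/-) |
| Outpatient entry with effusion or necrotizing/severe disease | n/a | Not separately listed |

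Row count: Appendix 1 has three groups of 8 rows (prior beta-lactam no with no severe allergy; prior beta-lactam no with severe allergy; prior beta-lactam yes with no severe allergy), so 24 rows. In each group only the 2 rows with neither effusion nor necrotizing/severe disease have an Outpatient entry. That leaves 3 × 6 = 18 rows marked n/a. This counts rows, not children.

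**2. What literal scoring does to later therapy**

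The SAP does not say whether a child's column is fixed at first disposition or moves with the child. It does not define the entire episode either; Protocol 7.2 defines only the index visit. Both column readings are therefore shown.

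| Later therapy | Column fixed | Column moves |
|---|---|---|
| Pathogen-directed change to a drug outside the child's row | Discordant | Discordant |
| Base row, ward: ampicillin, then oral amoxicillin while still on the ward | Discordant | Discordant |
| Base row, ward: ampicillin, then home on amoxicillin | Discordant if the discharge prescription counts | Concordant |
| Effusion row, ward: ampicillin, then home on an oral drug | Discordant if the prescription counts, unless the drug is in the Inpatient cell | Discordant if the prescription counts (n/a) |
| Base row, ventilated with shock: ceftriaxone plus vancomycin, vancomycin then stopped | Discordant if the cell requires both drugs | Concordant in ICU cells listing ceftriaxone alone; not in the Inpatient cell |

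Only the first two rows fail on both column readings. The others depend on definitions the SAP leaves open.

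**3. Reproducing the plan's figure**

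SAP 6.2.1 gives 750 per arm, 30% in usual care, a detectable difference of 6.8 points, alpha 0.05 and 80% power. Two-sided, pooled variance under the null:

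- SE under the null = √(2 × 0.334 × 0.666 / 750) = 0.02436
- SE under the alternative = √((0.30 × 0.70 + 0.368 × 0.632) / 750) = 0.02429
- z = (0.068 − 1.96 × 0.02436) / 0.02429 = 0.83, so power = 0.798

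The figure reproduces. It belongs to the primary outcome; no rate or power is stated for SO 1.

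**4. Can the understatement be sized?**

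Let *p* be the 24-hour rate, *a* the admitted share, and *r* the fraction of concordant admitted children still scored concordant over the episode. Assume that *p* is the same in admitted and discharged children, that discharged children keep their 24-hour status, and that *r* is equal in both arms. Then:

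SO 1 rate = *p* × [(1 − *a*) + *a* × *r*]

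The documents give no *r* and no planned *a*. The only admitted share is a background figure from 35 US children's hospitals (Protocol 1.0: median 31%, range 19–69%). The full range of *r* gives:

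| *a* | *r* = 1 | *r* = 0 | Difference at *r* = 0 |
|---|---|---|---|
| 19% | 30.0% v 36.8% | 24.3% v 29.8% | 0.068 × 0.81 = 5.5 points |
| 31% | 30.0% v 36.8% | 20.7% v 25.4% | 0.068 × 0.69 = 4.7 points |
| 69% | 30.0% v 36.8% | 9.3% v 11.4% | 0.068 × 0.31 = 2.1 points |

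These are outer limits under the assumptions, not estimates. Nothing in the documents places *r* within 0 to 1.

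**5. Direction between arms**

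Protocol 7.1 has the tool advise considering oral therapy on the ward. The base-row Inpatient cell does not list amoxicillin. If the advice is followed more often in intervention months, *r* would be lower in that arm and the SO 1 difference would shrink further. This is a possibility; its size is unknown.

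**The case against.** The strongest reply is that the SAP never expressly applies Appendix 1 to SO 1. The link is only a similarity of analysis, SAP 10.1 ties the table to the primary analysis, and SAP 4.2 drops the first-line wording. That is fair as far as it goes. But Appendix 1 is the only concordance rule in the SAP. If it does not govern, SO 1 has no rule and coders must supply one, so the same repair is needed.

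A second reply is that SAP version 1.1 records a clarification of the concordance definitions, so Appendix 1 may deliberately replace Table 1. Possibly so for the first 24 hours. Appendix 1 still does not say how later therapy is scored.

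A third reply is that receiving concordant therapy exclusively means no drug outside the list, so stopping one of two listed drugs is no deviation. This is a reasonable reading, and it is why de-escalation is only a possible misclassification here. Likewise, with a moving column, a base-row ward child sent home on amoxicillin scores concordant.

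A reader might also infer that SO 1 is artificially near zero in admitted children. The documents do not support that. Under the assumptions above, the control rate in admitted children is 0.30 × *r*. It reaches 3% only if *r* = 0.10, that is, if nine in ten concordant admitted children later leave their cell; at *r* = 0.50 it is 15%. Nor can a specific loss of power be claimed, since any flip fraction would be invented and SO 1 carries no power statement. SO 3 is not affected in the same way: it asks for any concordant therapy, so a child concordant at 24 hours already counts.

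**Conclusion.** The point holds in a limited form. Through its cross-reference to the primary analysis, SO 1 rests on a first-line table that conflicts with Protocol Table 1 on identified pathogens, ward amoxicillin and optional second agents, and that has no outpatient entry in 18 of 24 rows. A pathogen-directed change to a drug outside the row is scored discordant on either column reading. Some oral completion and de-escalation in admitted children may be as well, depending on the undefined episode, the column rule and how *plus* is read.

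The effect is to understate SO 1 by an amount that cannot be computed from the documents, possibly by different amounts in the two arms. The Phase 1 power statement is unaffected. SO 1 is a secondary outcome analysed without alpha adjustment (SAP 7.2), so this should be fixed but does not threaten the primary conclusion.

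**What to change.** Before outcome coding, amend SAP 10.2 and Appendix 1 for SO 1:

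1. Reconcile Appendix 1 with Protocol Table 1 and state which governs SO 1.
2. Carry the Table 1 exemption (identified pathogen or known drug allergy) into SO 1 scoring, so that therapy after a pathogen is identified is not coded discordant.
3. Define the entire episode, including whether a prescription at hospital discharge counts.
4. State whether the disposition column is fixed or moves with the child.
5. Have the investigators settle how oral completion (including the rows now marked n/a) and a dropped component of a *plus* regimen are scored. The rules should be identical in both arms and settled blind to arm. SAP 6.3.1 leaves study staff unblinded, and the SAP mentions blinded outcome review only for Phase 2. This review does not propose any regimen.

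Leave SO 3 unchanged.

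The cost is SAP wording and some table entries. SAP 10.1 already captures the antibiotic information by chart review, and SAP 7.1 lists medication orders and prescriptions among the data collected. The downside is that SO 1 becomes somewhat less strict than a literal reading of Appendix 1.
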